11.2 Analysis Plan

The **Safety Population** will consist of all participants who received any amount of either product, and on whom any post-randomization safety information is available.

The Intention-to-Treat (ITT) Population consists of all participants who are randomized to a study group.

The **Per Protocol (PP) Population** consists of all participants who consumed at least 80% of investigational product or placebo doses, do not have any protocol deviations that affect primary outcomes and complete all study visits and procedures connected with measurement of the primary variable.

11.3 Statistical Analysis Plan

For both count and continuous primary and secondary outcomes, summary statistics including number of participants, mean, median, standard deviation, first quartile, third quartile, minimum, and maximum will be obtained for each available time interval and for each group. For categorical outcomes, frequencies and percentages will be presented.

The difference in the number of incidences of URTI, duration days of URTI, missed school days, well days, illness days between Bacillus coagulans SNZ 1969 and Placebo groups will be assessed by computing the rate ratio with 95% confidence interval using a generalized linear model with log link function (Poisson or negative binomial regression model).

The difference in the number of incidences of Additional Respiratory Symptoms and the duration days of Additional Respiratory Symptoms between Bacillus coagulans SNZ 1969 and Placebo groups will be assessed by computing the rate ratio with 95% confidence interval using a generalized linear model with log link function (Poisson or negative binomial regression model).

The difference in the number of incidences of GITI symptoms, duration days of GITI symptoms, missed school days, well days, illness days between Bacillus coagulans SNZ 1969 and Placebo groups will be assessed by computing the rate ratio with 95% confidence interval using a generalized linear model with log link function (Poisson or negative binomial regression model).

The difference in the AUC for daily total CARIFS scores, the mean total severity scores of URTI symptoms, the AUC for daily total Additional Respiratory Tract Symptoms questionnaire scores, the AUC of GITI symptom scores, and mean of GITI symptom scores between Bacillus coagulans SNZ 1969 and Placebo groups will be assessed by two-sample t-test if the outcome is normally distributed and Wilcoxon's rank sum test if the outcome is not normally distributed. Normality assumption will be assessed using quantile-quantile (Q-Q) plots.

Fisher's exact test will be used to assess the difference of proportion of participants who used prescription and non-prescription cold/flu medications to treat URTI/GITI symptoms between Bacillus coagulans SNZ 1969 and Placebo. 95% confidence interval of odds ratio will be calculated.

Differences between groups for sIgA, IgA, IgG, IgE, IgM, and immune response biomarkers at day 84 will be assessed by ANCOVA model adjusting for baseline values.

To assess the goodness of fit of the log link models, the Poisson regression model and the negative binomial regression model will be applied to the same dataset and then the Likelihood Ratio Test will be performed. If the p-value of the test is less than 0.05, then we will use the negative binomial model as it offers a better fit of the count data.

To evaluate the adequacy of ANCOVA model, diagnostics including Q-Q plots (for assessing the normality of error terms) and plots of residuals versus fitted values (to examine if the residuals are independent and have constant variance) will be generated. If these diagnostic plots indicate deviations from the model's assumptions, ranks or other transformation of the dependent variable, will be implemented.

Two-sided probabilities ≤ 0.05 will be considered statistically significant. All statistical analysis will be completed using the R Statistical Software Package Version 4.3.2 or newer for Microsoft Windows.

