5 STUDY OBJECTIVES

The objective of this study is to investigate the safety and efficacy of *Bacillus coagulans* SNZ 1969 on the incidence rate, duration, and severity of acute upper respiratory tract infections (URTI) and gastrointestinal tract infection (GITI) symptoms in healthy school-aged children.

Primary outcomes:

- 1. The difference in incidence, duration, and severity (area-under-the-curve (AUC)) of URTI as assessed by the Canadian Acute Respiratory Illness and Flu Scale (CARIFS) from baseline to day 84 between *Bacillus coagulans* SNZ 1969 and placebo
- 2. The difference in incidence, duration, and severity (area-under-the-curve (AUC)) of Additional Respiratory Tract Symptoms as assessed by Additional Respiratory Tract Symptoms questionnare from baseline to day 84 between *Bacillus coagulans* SNZ 1969 and placebo
- 3. The difference in incidence, duration, and severity (AUC) of GITI symptoms as assessed by the GITI Symptoms Questionnaire from baseline to day 84 between *Bacillus coagulans* SNZ 1969 and placebo

Secondary outcomes:

[figure not shown]
- 1. The difference in incidence, duration, and severity (AUC) of URTI as assessed by the CARIFS from baseline to days 28 and 56 between *B coagulans* SNZ 1969 and placebo
- 2. The difference in incidence, duration, and severity (AUC) of Additional Respiratory tract symptoms as assessed by Additional Respiratory Tract Symptoms questionnare from baseline to days 28 and 56 between *B coagulans* SNZ 1969 and placebo
- 3. The difference in incidence, duration, and severity (AUC) of GITI symptoms as assessed by the GITI Symptoms Questionnaire from baseline to days 28 and 56 between *B. coagulans* SNZ 1969 and placebo
- 4. The difference between *B. coagulans* SNZ 1969 and placebo from baseline to days 28, 56, and 84 on:
 - a. Severity of cold/flu and GITI symptoms as assessed by total and individual daily symptom scores
 - b. Number of missed school days
 - c. Number of well days, related to the absence of cold/flu and GITI symptoms
 - d. Use of prescription and non-prescription cold/flu medications to treat cold or flu symptoms
 - e. Total days of illness
- 5. The difference in change between B. coagulans SNZ 1969 and placebo from baseline to day 84 on:
 - a. Saliva secretory immunoglobulin A (sIgA) concentrations
 - b. Serum levels of Immunoglobulin A (IgA), G (IgG), E (IgE) and M (IgM)

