9.7.6 Study Diary

Participant caregiver's will be instructed to complete the study diary daily. Questions pertaining to IP compliance, lifestyle habits, concomitant medications (inclusive of OTC medications and vaccinations), tracking cold/flu and GITI symptoms (see Sections 9.7.7, 9.7.8, and 9.7.9 below), missed school days, and any adverse events and symptoms throughout the study will be included. Each day, caregivers will ask if their child has any of the symptoms listed in the CARIFS, Additional Respiratory Tract Symptoms or GITI Symptom Questionnaires (Sections 16.1, 16.2, and 16.3). Caregivers will report all symptoms in the study diary daily using the CARIFS, Additional Respiratory Tract Symptoms, and GITI Symptoms Questionnaires.

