11 STATISTICAL EVALUATION

11.1 Determination of Sample Size

Assuming placebo participants would experience 1.43 episodes of URTIs and 7.42 duration days of URTI symptoms during 84 days of follow up (22), a sample size of 100 participants (50 participants per arm) has a power of 80% to detect a rate of \leq 0.76 for the number of episodes of URTIs and \leq 5.80 for the duration days of URTI symptoms in the Bacillus coagulans SNZ 1969 group using Poisson regression model.

In addition, a sample size of 100 participants could detect an effect size ≥ 0.63 in the AUC of GITI symptom scores and in the AUC of the Additional Respiratory Tract Symptoms questionnaire, and a difference of ≥27.8 score.day in the mean of AUC of CARIFS daily total symptom scores between Bacillus coagulans SNZ 1969 and placebo groups assuming standard deviations equal to 52.96 and 32.85 score.day for Bacillus coagulans SNZ 1969 and placebo groups (22), respectively, using two-sample t-test with 80% power, 2-sided 5% significance level, and 20% dropout rate.

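### Well days are capped by the diary days, but section 11.3 allows only Poisson or negative binomial models for them, and neither suits a bounded count

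*Protocol*

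**What the plan says.** Section 5 lists secondary outcome 4c as "Number of well days, related to the absence of cold/flu and GITI symptoms", to be compared from baseline to days 28, 56 and 84. Section 9.7.6 fixes the unit of observation: "Participant caregiver's will be instructed to complete the study diary daily". Well days are therefore a count out of roughly 28, 56 or 84 diary days, give or take the two-day visit window.

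Section 11.3 names well days in two of its lists, once with the URTI outcomes ("duration days of URTI, missed school days, well days, illness days between Bacillus coagulans SNZ 1969 and Placebo groups") and once with the GITI outcomes. Both lists are to be analysed by a "rate ratio with 95% confidence interval using a generalized linear model with log link function (Poisson or negative binomial regression model"). For the choice between the two models, a likelihood ratio test is run: "If the p-value of the test is less than 0.05, then we will use the negative binomial model". Section 11.3 gives the ANCOVA models a fallback (ranks or another transformation) but gives the count models none. It mentions no offset or denominator for well days.

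**The concern.** A Poisson model fixes the variance at the mean, and a negative binomial model adds to it. A count that sits near a ceiling can have a variance well below its mean, and the selection rule has no route for that case. The standard error is then too large, the test too conservative, and a real benefit can be missed. Neither model knows that a child cannot have more well days than diary days.

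This is a stated choice of model rather than a detail left for later. A statistical analysis plan would have to replace it, not merely complete it. At stake is the interpretation of one named secondary outcome at three time points, in particular whether a null result on well days means anything.

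**Working it through.** **Inputs.** From section 11.1: "1.43 episodes of URTIs and 7.42 duration days of URTI symptoms during 84 days of follow up" on placebo; detectable rates of 0.76 episodes and 5.80 days on active; 50 per arm; 20% dropout, so 40 per arm evaluable; 5% two-sided. Not given, hence assumed: the SD of ill days (2.7 to 20), the episode-length distribution, the frequency of GI symptoms, and the timing of dropout.

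**1. The protocol's own power.** Power = Φ(|ln(λ1/λ0)| / √(1/(nλ0) + 1/(nλ1)) − 1.96) with n = 40.
- Episodes: 0.632/0.2245 = 2.816, power 80.4%.
- Duration days: 0.2463/0.0876 = 2.811, power 80.3%.

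The stated 80% is reproduced. No power is stated for well days.

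**2. The same figures as well days.** 84 − 7.42 = 76.58 and 84 − 5.80 = 78.20, so the rate ratio is 78.20/76.58 = 1.021. With 50 per arm the Poisson standard error of the log ratio is √(1/(50 × 76.58) + 1/(50 × 78.20)) = 0.0227, and the expected z is 0.0209/0.0227 = 0.92. If ill days were Poisson, as section 11.1 treats them, their variance would be 7.42. The true standard error would then be √(7.42/76.58) = 0.31 of the model's. Type I error would be practically zero and power about 0.1% or less. The same data analysed as ill days have about 88 to 89% power. Only the model differs.

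**3. Dependence on the unknown SD.** Under Poisson, type I error = 2Φ(−1.96/√(V/76.58)), where V is the true variance. This gives 0.06% at SD 5, 3.2% at SD 8 and 5% at SD 8.75 (V = 76.58). Simulating the full section 11.3 rule (50 per arm, complete follow-up, mean 7.42 ill days, binomial or beta-binomial out of 84) gave:

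| SD of ill days | Type I error, 11.3 rule | Power, 11.3 rule (7.42 vs 5.80) | Power, quasi-binomial |
|---|---|---|---|
| about 2.7 | 0% | 0.1% | 89% |
| 5 | 0% | 2.4% | 43% |
| 8 | 3.3% | 11% | 21% |
| 10 | 4.3% | 14% | 14% |
| 12 | 4.5% | – | 11% |
| 15 | 2.0% | – | – |
| 20 | 0.1% | – | – |

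With a mean of 15 or 25 ill days and SD 8 to 12, type I error was 4.1 to 6.2%. The quasi-binomial held 4.8 to 6.1% for SDs of 2.7 to 12, with or without 20% dropout.

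**4. Episode-based simulation.** Episodes are Poisson, 1.43 vs 0.76. Mean length is 7.42/1.43 = 5.2 days (two days plus a geometric part, assumed). There are 40 complete diaries per arm. The effect is 7.42 vs 7.42 × 0.76/1.43 = 3.94 ill days, larger than in step 3.

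| Setting | Type I error, 11.3 rule | Power, 11.3 rule | Power, proportion with empirical variance |
|---|---|---|---|
| URTI days only | about 1% | 28% | 65% |
| plus GI symptoms on 5% of days | 4–7% | 29% | 30% |
| plus GI symptoms on 20% of days | 4–7% | 13% | 16% |

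In the URTI-only setting the proportion analysis had about 5% type I error. The variance of well days was about 44 to 46 at a mean of 77. That variance comes from the assumed lengths together with overlap and truncation at Day 84; without those two it would be about 58.

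**5. Withdrawals, if no denominator is used.** With 50 per arm, 20% leaving on a random day and URTI days only, the rule gave 3% power, against 68% for the proportion. If withdrawal were 10% in one arm and 20% in the other, at mid-study on average, the ratio with no true effect would be (1 − 0.20 × 0.5)/(1 − 0.10 × 0.5) = 0.90/0.95 = 0.95. That is further from 1 than the 1.021 in step 2. An offset alone does not repair the variance: Poisson with a log(days) offset gave 0% type I error at SD 2.7 and 7 to 8% at SD 10.

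**The case against.** The strongest objection is that the loss is not general. Well days also require the absence of 13 GITI items, among them flatulence, burping and bad breath, so URTI-only means and variances are not those of this outcome. Once ill days become more frequent and variable, the rule is close to its nominal size and the proportion analysis gains little (step 4). A reader might infer from the URTI-only figures that the test is always far too conservative. The protocol gives no SD to support that, and steps 3 and 4 show it is untrue for SDs of about 8 to 12. This part of the objection stands.

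A second objection is that the protocol nowhere says withdrawn children are analysed on raw days. A reader might infer that every withdrawal is scored as sick days. The text does not say so: it reports a rate ratio, which can carry an offset for days observed, and such detail often sits in a statistical analysis plan, which is not at hand. This stands too, so step 5 is a conditional risk and not a rule of the protocol.

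Neither objection rescues the pair of models. A bounded count has been assigned to two unbounded ones, and the selection rule moves in one direction only.

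**Conclusion.** The point holds as a wrong choice of model for one secondary outcome. How much it matters cannot be fixed from the protocol. The loss is severe if ill days are few and vary little: about 1% type I error, and 28% power where 65% is available, under the assumed episode lengths and 1.43 vs 0.76 episodes. It is small if GI symptoms on 5 to 20% of days dominate and diaries are complete. At the assumed 20% dropout nearly all power would be lost, but only if well days were analysed without a denominator, on which the protocol is silent. No primary outcome and no part of the sample size calculation depends on this.

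**What to change.** In section 11.3, take well days out of both Poisson/negative binomial lists. Analyse well days divided by completed diary days, with a quasi-binomial (logit) model or a between-arm difference with empirical variance. Report the difference in percent of diary days well with a 95% confidence interval. State that completed diary days are the denominator for children who withdraw. Add that illness days (4e) are essentially the complement of well days, provided an illness day means a diary day with symptoms, so that the two are read as one comparison and not as independent results.

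The cost is one paragraph, before unblinding. The rate ratio gives way to a percent difference, and unobserved days are assumed to resemble observed ones.

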9.2 Run-in (Day -14 to Day -1)

Participants will complete the study diary inclusive of the CARIFS, Additional respiratory tract symptoms, and GITI symptoms questionnaires during the 14-day run-in period.

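### The primary severity outcomes get an unadjusted test chosen from a Q-Q plot, although a 14-day run-in score on the same questionnaires is collected and the CARIFS AUC is powered only as a mean difference

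*Protocol*

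**What the plan says.** Section 5 lists severity, as AUC, among the primary outcomes for all three questionnaires. Sections 9.7.7 to 9.7.9 add a mean score as a second way of calculating severity.

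Section 11.3 states that the AUCs and the URTI and GITI mean scores "will be assessed by two-sample t-test if the outcome is normally distributed". If the outcome is not normal, Wilcoxon's rank sum test replaces the t-test. Normality is judged from Q-Q plots, and no criterion is given.

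For incidence and duration, Section 11.3 names a Poisson or negative binomial model with log link and lists no covariates. For sIgA, the serum immunoglobulins and the immune biomarkers, the same section says that group differences "at day 84 will be assessed by ANCOVA model adjusting for baseline values".

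Section 9.2 provides the pre-randomisation data: "Participants will complete the study diary inclusive of the CARIFS, Additional respiratory tract symptoms, and GITI symptoms questionnaires during the 14-day run-in period".

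Section 11.1 bases the severity power on "a sample size of 100 participants (50 participants per arm" in total, "using two-sample t-test with 80% power, 2-sided 5% significance level, and 20% dropout rate". The CARIFS target is a difference of 27.8 "score.day in the mean of AUC of CARIFS daily total symptom scores", "assuming standard deviations equal to 52.96 and 32.85 score.day" for active and placebo. For GITI and Additional Respiratory AUC the target is a standardised effect of "0.63 in the AUC of GITI symptom scores".

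**The concern.** There are two linked issues.

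**Unused baseline.** The run-in gives each child a pre-randomisation score on the instruments that define the primary severity outcomes. The AUCs are not confined to illness episodes: they accumulate daily scores. Several items (flatulence, constipation, halitosis, sneezing, itchy nose, poor sleep) could differ between children in a lasting way. If so, the run-in score predicts the follow-up AUC. Leaving it out then gives up precision and leaves chance imbalance between the arms uncorrected. The plan adjusts secondary laboratory markers for baseline and does not say why the primary scores are treated differently.

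**Unfixed estimand.** A t-test addresses a difference in means and Wilcoxon's test a shift in ranks. Until the plot has been read, nobody can say which of these the primary severity result will report. Under the Wilcoxon branch, the mean difference powered in Section 11.1 is not what is tested.

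**Working it through.** **1. Reproduce the stated size (inputs from Section 11.1).**
- Root-mean-square SD = √[(52.96² + 32.85²)/2] = 44.07.
- CARIFS AUC, normal approximation: n = 2 × (1.960 + 0.842)² × 44.07² / 27.8² = 39.4, so 40 per arm.
- Standardised effect 0.63: n = 2 × (1.960 + 0.842)² / 0.63² = 39.6, so 40 per arm.
- With 20% dropout: 40 / 0.80 = 50 per arm, 100 in total. This matches the protocol.
- By the noncentral t distribution with 40 per arm, power is 79.6% at 27.8 and 79.5% at 0.63. The difference detectable with 80% power is 27.95.

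The stated size is therefore that of an unadjusted t-test.

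**2. Effect of adjusting for the run-in score.** With correlation r between run-in score and follow-up AUC, the residual SD is 44.07 × √(1 − r²). The protocol gives no r, so a range is shown. The same r is assumed in both arms, with 40 evaluable per arm.

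| r (assumed) | Variance removed (r²) | Residual SD | Power at 27.8 | Difference detectable at 80% |
|---|---|---|---|---|
| 0 | 0% | 44.07 | 79.6% | 27.95 |
| 0.2 | 4% | 43.18 | 81.2% | 27.4 |
| 0.3 | 9% | 42.04 | 83.2% | 26.7 |
| 0.4 | 16% | 40.39 | 86.0% | 25.6 |
| 0.5 | 25% | 38.16 | 89.6% | 24.2 |

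The degree of freedom spent on the covariate changes power only in the fourth decimal place.

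**3. Chance imbalance.** With 50 per arm, the standardised difference in a baseline score has standard error √(2/50) = 0.20. The probability that it exceeds 0.3 in either direction is 2 × [1 − Φ(0.3/0.20)] = 13%.

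**4. What the run-in cannot supply.** At the placebo rate of 1.43 URTI episodes per 84 days, 14 days yield 1.43 × 14/84 = 0.24 expected episodes. Under a Poisson model, exp(−0.24) ≈ 79% of children have none. Most children therefore have no run-in episode duration or per-episode severity. The mean daily score exists for all who keep the diary, but it is a different quantity.

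**5. Is the Wilcoxon branch realistic?** At the Section 11.1 rates, a Poisson model gives exp(−1.43) = 24% of placebo children and exp(−0.76) = 47% of active children with no URTI episode. That points towards skewed CARIFS AUCs, so the branch may well be used.

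**6. Does the switch inflate type I error?** In null simulations (40 per arm; normal, skewed and zero-inflated skewed data; 20,000 runs each), each test alone rejected in about 5%. A fixed normality rule, with Shapiro-Wilk standing in for the plot, also gave about 5%. Always taking the smaller p-value, the upper bound for an unfixed choice, gave about 6% to 7%.

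**The case against.** The strongest case on the other side is that nothing here is invalid. Randomisation makes the unadjusted comparison unbiased, and Section 11.1 was calculated for exactly that test. A reader might infer that the trial is biased or undersized. Neither follows, because the planned power and the planned test agree.

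A reader might also infer that every primary outcome is left unadjusted. The text supports this only for the severity outcomes, where the named tests cannot take a covariate. The log-link models list no covariates but exclude none, and a separate SAP may name one.

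The benefit may be small. Enrolment is of healthy children, and asthma, severe environmental allergies and clinically relevant gastrointestinal or respiratory disorders are excluded. That narrows lasting differences in symptoms. A Poisson model without differences between children implies zero correlation for episode counts. That habitual symptoms persist is plausible for GITI scores, but the protocol gives no data on it.

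Baseline ANCOVA for the laboratory markers is not a contradiction either: those are single measurements at Day 0 and Day 84, whereas the primary outcomes accumulate over the follow-up.

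On the test choice, a reader might infer an inflated false-positive rate. The direction of the rule is fixed in advance, a fixed rule holds about 5%, and Section 14.3 gives the statistician a locked, blinded database.

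All of this stands. It limits the size of the point but leaves two facts untouched: the collected run-in score cannot enter the tests named for severity, and the effect measure depends on a plot with no stated criterion.

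**Conclusion.** The point holds as a worthwhile improvement to the severity analysis; it does not show an error in the design. The sample size reproduces and the planned comparison is unbiased. Adjustment would lift power at 27.8 score.day from about 80% to 81% at a correlation of 0.2, 86% at 0.4 and 90% at 0.5. These correlations are assumptions. The gain may be small for CARIFS and for the URTI episode measures, and is more plausible for GITI AUC. The second benefit does not depend on any correlation: one named analysis keeps the CARIFS result on the mean difference that was powered. For the count and duration models, the point is only that no covariate is currently stated.

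**What to change.** In Section 11.3:
- Name one primary analysis for the severity outcomes: ANCOVA with the run-in mean daily score on the same questionnaire as covariate and heteroscedasticity-robust standard errors. Robust errors suit the unequal SDs that Section 11.1 assumes.
- Keep Wilcoxon's test as a sensitivity analysis and delete the Q-Q-plot switch for these outcomes.
- State that the later rule in Section 11.3, which allows ranks or another transformation when ANCOVA diagnostic plots look poor, does not apply to this primary analysis. Otherwise the plot-driven choice returns by another route.
- Name the run-in mean score or number of symptom days as a covariate in the log-link models.

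Age and calendar-month covariates are not needed for this purpose. The cost is wording in Section 11.3 or the SAP, settled before unblinding. No new data are needed and the sample size does not change.

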The current study will examine the efficacy of *Bacillus coagulans SNZ 1969 (B. coagulans)* on immune health in children attending school. The primary outcome will assess the difference between the investigational product and placebo from baseline to day 84 in incidence, duration, and severity of (1) Upper Respiratory Tract Infection (URTI) and (2) Gastrointestinal Tract Infection (GITI) symptoms. This will be assessed by use of the Canadian Acute Respiratory Illness and Flu Scale (CARIFS) and a GITI symptoms questionnaire. A randomized, double-blind placebo controlled study of healthy school aged children (6-8

years) evaluating *B. coagulans* demonstrated a significant decrease in incidence of Upper Respiratory Tract Infections (URTIs) symptoms including nasal congestion, bloody nasal mucus, itchy nose, and hoarseness (17). There were corresponding decreases in duration of URTI symptoms of hoarseness, headache, red eyes and fatigue (17). In the same study *B. coagulans* significantly decreased the incidence of flatulence, a potentially symptom of GITI. These beneficial effects were associated with modulation of serum immune markers for TNFα, CD163, G-CSF, ICAM-1, IL-6, IL-8, MCP-2, RAGE, uPAR, and PF4 (17). Similarly, a randomized double blind placebo control study of malnourished children between 1 and 5 years of age demonstrated a significant reduction in the total days of illness with *B. coagulans SNZ 1969*® compared to placebo over a period of 3 months (18). This study also demonstrated a non-significant reduction gastrointestinal and respiratory tract infections along with a shorter duration of infection (18).

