 - c. Immune response biomarkers: CD14, CD163, CD40 (TNFRSF5), CRP (C-Reactive Protein), E-Selectin, Fas (TNFRSF6/Apo-1), Fas Ligand (TNFSF6), GCSF, ICAM-1 (CD54), IL-1 alpha (IL-1 F1), IL-1 beta (IL-1 F2), IL-1 R4 (ST2), IL-10, IL-12 p70, IL-13, IL18, IL-2, IL-2 R alpha, IL-4, IL-6, IL-8 (CXCL8), Lipocalin-2 (NGAL), MCP-1 (CCL2), MCP-2 (CCL8), MIF, MIP-1 alpha (CCL3), MIP-1 beta (CCL4), Osteopontin (SPP1), PAI-1, Platelet Factor 4 (CXCL4), Procalcitonin, RAGE, Resistin, Thrombomodulin, TNF alpha, TREM-1, Troponin I, uPAR, VCAM-1 (CD106), VEGF-A.
 - d. Microbiome as assessed by 16s rRNA fecal microbiome analysis

Safety outcomes:

- 1. Incidence of post-emergent adverse events (AE)
- 2. Clinically relevant changes in vital signs (blood pressure (BP) and heart rate (HR)) after supplementation

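### The protocol's single p ≤ 0.05 rule covers 45 secondary immune markers without multiplicity control, so 2.25 false-positive markers are expected on average if the product affects none of them

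*Protocol*

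**What the plan says.** Protocol section 5 places the immune markers under "Secondary outcomes", item 5, as differences in change between groups from baseline to Day 84. Three entries matter here:

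- Item 5a: "Saliva secretory immunoglobulin A (sIgA) concentrations", one marker.
- Item 5b: "Serum levels of Immunoglobulin A (IgA), G (IgG), E (IgE) and M (IgM"), four markers.
- Item 5c: an array panel that begins "Immune response biomarkers: CD14, CD163, CD40 (TNFRSF5), CRP (C-Reactive Protein), E-Selectin, Fas (TNFRSF6/Apo-1), Fas Ligand (TNFSF6), GCSF" and runs on to VEGF-A, 40 proteins by count.

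Section 11.3 gives the analysis: "Differences between groups for sIgA, IgA, IgG, IgE, IgM, and immune response biomarkers at day 84 will be assessed by ANCOVA model adjusting for baseline". The same section closes with a decision rule that does not distinguish primary from secondary outcomes: "Two-sided probabilities ≤ 0.05 will be considered statistically significant". Nowhere does the protocol rank the markers, make their testing depend on the primary outcomes, control a familywise or false discovery rate, or call the panel exploratory.

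**The concern.** A threshold of 0.05 limits the error of one test. Here it is applied to 45 tests that address one broad question, whether the product changes immune markers. Read as written, section 11.3 calls each marker that reaches p ≤ 0.05 statistically significant. A report that follows it could present a few markers as changed by the product when chance alone would produce that many. The reader would have no stated means of telling these from real effects.

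The Introduction shows how such results may be used. It links the symptom benefits in an earlier trial to "modulation of serum immune markers for TNFα, CD163, G-CSF, ICAM-1, IL-6, IL-8, MCP-2, RAGE, uPAR, and PF4". A similar reading of this trial's panel is foreseeable, although the protocol does not commit to one. Correcting multiplicity among the primary symptom outcomes would not correct it here, because the markers form a separate family.

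**Working it through.** **Inputs**

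- Number of tests: 1 (sIgA) + 4 (IgA, IgG, IgE, IgM) + 40 (array) = 45, from section 5, items 5a to 5c. The microbiome, item 5d, is not counted.
- Per-test level: 0.05, two-sided, from section 11.3.
- Evaluable participants: 50 per arm with 20% dropout gives 50 × 0.8 = 40 per arm, from section 11.1.
- Correlation between markers: not given. It is assumed common to all pairs and varied from 0 to 0.8.

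**The plan's own figure.** The protocol states no error rate for the marker family. Its stated figure is 80% power to detect an effect size of 0.63 at two-sided 5%. With 40 per arm, the detectable effect is (1.960 + 0.842) × √(2/40) = 0.626 by the normal approximation, and 0.634 by the t distribution. Power at 0.63 is 80.4% and 79.5% respectively. The figure reproduces, and it confirms that 0.05 is a level for a single test.

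**Expected false positives.** If no marker is affected, the expected number is 45 × 0.05 = 2.25. Expectations add whatever the dependence, so this needs no correlation assumption.

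**Chance of at least one, independent tests.** 1 − 0.95^45 = 0.901.

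**Chance of at least one, correlated tests.** The test statistics are taken as equicorrelated normal with all effects zero:

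| Common correlation | At least one false positive | Two or more | Median number |
|---|---|---|---|
| 0 | 90% | 67% | 2 |
| 0.3 | 78% | 50% | 2 |
| 0.5 | 60% | 37% | 1 |
| 0.6 | 49% | 31% | 0 |
| 0.8 | 29% | 21% | 0 |

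The first probability crosses 50% at a correlation of about 0.59. Put another way, the panel would have to behave like fewer than ln 0.5 / ln 0.95 = 13.5 independent tests for it to fall below 50%.

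**Check with the planned model.** A simulated null ANCOVA with 40 per arm (assumed baseline correlation 0.5, 3,000 replicates) gave 89%, 78%, 61% and 40% at marker correlations of 0, 0.3, 0.5 and 0.7. Five blocks of nine markers, correlated 0.7 within and 0.2 between blocks, gave 66%.

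**Under the proposed rule.** With Benjamini-Hochberg at 5% over the 45 markers and no true effects, the chance of any false call is 5.0%, 4.5%, 3.6% and 2.1% at correlations of 0, 0.3, 0.5 and 0.8.

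**Price in power.** The strictest simple alternative, Bonferroni at 0.05/45 = 0.00111, would raise the effect detectable with 80% power from 0.63 to about 0.95 standard deviations (two-sample t-test, 40 per arm). Benjamini-Hochberg is never stricter than that.

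**The case against.** The strongest reply is that multiplicity handling for a secondary panel is commonly left to a separate statistical analysis plan, which is not at hand. The threshold sentence can also be read as a generic per-test level: it does not say that p-values will be unadjusted, and it ties no claim to any marker. This has weight. It does not remove the point, because the protocol is not silent. It states the decision rule in its own section 11.3 and applies it without exception, so a later plan that added false discovery control would be changing the rule as a reader now finds it.

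It can also be said that the markers matter little here. The stated objective concerns symptom incidence, duration and severity, the markers are the fifth secondary item, and the sample size does not use them. That stands, and it limits the severity.

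Four stronger readings are tempting, and the documents do not support them:

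- A reader might infer that a false marker finding is more likely than not, or that about two will typically be reported. Both depend on correlations that the protocol does not give. The mean of 2.25 is fixed, but the median falls to 1 at a correlation of 0.5 and to 0 at 0.6.
- A reader might divide 90% by 5% and say that the stated error rate is exceeded many times over. The stated 0.05 is a per-test level, and no familywise level is stated for the markers.
- A reader might extend the calculation to the Day 28 and Day 56 symptom outcomes by multiplying questionnaires, measures and time points. Sections 9.7.7 to 9.7.9 define two severity methods and, for two of the questionnaires, outcomes symptom by symptom. Objective 4 adds more, and data to Day 28 are contained in data to Day 56. No simple count describes that family.
- A reader might fault the protocol for not testing first the ten markers named in the Introduction. Reference 17 shows that they come from a trial of a different *B. coagulans* strain (GBI-30, 6068), so they are a weak basis for ranking markers in a trial of SNZ 1969.

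**Conclusion.** The concern holds in a limited form. Section 11.3 as written applies an unadjusted 5% rule to 45 secondary immune markers, which gives 2.25 expected false positives if none is affected. The chance of at least one ranges from 90% (independence) to 29% (common correlation 0.8), and is above one half only below about 0.59. The mean rests only on the count of 45 and the per-test level. The probabilities also rest on the assumed equal correlation. Severity is moderate to low: no stated success criterion and no part of the sample size depends on these markers, so the risk lies in how the marker results are described.

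**What to change.** In section 11.3:

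1. For the 45 markers, report each between-group estimate with its 95% confidence interval and a Benjamini-Hochberg adjusted p-value (5% false discovery rate across all 45).
2. Restrict the threshold sentence so that a marker is called statistically significant only on its adjusted value.
3. State that all secondary outcomes, including the Day 28 and Day 56 symptom comparisons, are supportive and not a basis for efficacy claims.

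This takes a few sentences and one function call in R, which the protocol already names as its software. No visit, sample or sample size changes. The cost is lower power per marker and fewer nominally significant markers in the report.
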